10.6 Appendix 6: Country-specific Requirements

This appendix is not applicable to this study.

10.7 Appendix 7: 12-Lead Electrocardiogram Abnormality Criteria

| 12-Lead Electrocardiogram Abnormality Criteria | | |
|--|---|---|
| | Screen Failure Criteria | Potentially Significant Post-randomization Findings (clarification on action to take) |
| RHYTHM | | |
| Sinus Tachycardia | >110 bpm | HR >110 bpm and HR increase of ≥ 25 bpm from baseline |
| Sinus Bradycardia | <40 bpm | HR <40 bpm and HR decrease of ≥ 5 bpm from baseline |
| Sinus Pause/Arrest | >2.0 seconds | >2.0 seconds |
| Atrial Premature Complex | > 1 beat | ≥ 3 beats |
| Ventricular Premature Complex | All | ≥ 3 beats |
| Ectopic Atrial Rhythm | None | None |
| Junctional Rhythm | Junctional Rhythm with HR <40 bpm | Junctional Rhythm with HR <40 bpm |
| Idioventricular Rhythm | All | All |
| Atrial Fibrillation | All | All |
| Atrial Flutter | All | All |
| Supraventricular Tachycardia | All | All |
| Ventricular Tachycardia | All | All |
| AXIS | | |
| Left Axis Deviation | RBBB With Left Anterior Hemiblock (LAHB) | New Onset LAHB |
| Right Axis Deviation | RBBB With Left Posterior Hemiblock (LPHB) | New Onset LPHB |
| CONDUCTION | | |
| 1st Degree AV Block | PR ≥ 230 ms | PR ≥ 230 ms + Increase of >15 ms; or PR Increase of >25% |
| 2nd Degree AV Block | Mobitz Type II | Mobitz Type II |
| 3rd Degree AV Block | All | All |
| LBBB | All | All |
| RBBB | RBBB With LAHB/LPHB as Defined Above | New Onset RBBB (Not Including Rate-related) |
| Incomplete Right BBB (ICRBBB) (QRS <120 ms) | No Exclusion | Nothing |
| Short PR/ Preexcitation Syndrome | Delta Wave + PR <120 ms | Delta Wave + PR <120 ms |
| Other Intra-Ventricular Conduction Delay | QRS ≥ 130 ms | QRS ≥ 130 ms + Increase of ≥ 10 ms |
| QTc (B or F) | | |
| Male | QTc ≥ 470 ms | QTc ≥ 500 ms or Increase of ≥ 60 ms From Baseline |
| Female | QTc ≥ 480 ms | QTc ≥ 500 ms or Increase of ≥ 60 ms From Baseline |

| 12-Lead Electrocardiogram Abnormality Criteria | | |
|--|---|---|
| | Screen Failure Criteria | Potentially Significant Post-randomization Findings (clarification on action to take) |
| HYPERTROPHY | | |
| Atrial Abnormalities | Definite Evidence of P Mitrale or P Pulmonale | Definite Evidence of P Mitrale or P Pulmonale |
| Ventricular Abnormalities | Voltage Criteria for LVH Plus Strain Pattern | Voltage Criteria for LVH Plus Strain Pattern |
| MYOCARDIAL INFARCTION | | |
| Acute or Recent | All | All |
| Old | All | All |
| ST/T MORPHOLOGY | | |
| ST Elevation Suggestive of Myocardial Injury | In 2 or more contiguous leads | In 2 or more contiguous leads |
| ST Depression Suggestive of Myocardial Ischaemia | In 2 or more contiguous leads | In 2 or more contiguous leads |
| T-wave Inversions Suggestive of Myocardial Ischaemia | In 2 or more contiguous leads | In 2 or more contiguous leads |
| Non-specific ST-T Changes (In 2 or More Leads) | No exclusion | In 2 or more contiguous leads |
| PACEMAKER | All | All |
| Baseline is defined as Predose Day 1; ms=milliseconds, mm=millimeter | | |

10.8 Appendix 10.8: Algorithm for Assessing Out of Range Laboratory Values

For all laboratory values obtained at prestudy (screening) visit and/or predose evaluation:

- A. If all protocol-specified laboratory values are normal, the participant may enter the study.
- B. If a protocol specified laboratory value is outside of the parameter(s) outlined in the inclusion/exclusion criteria (including a repeat if performed), the participant will be excluded from the study.
- C. If ≥ 1 protocol-specified laboratory value not specified in the inclusion/exclusion criteria is outside the normal range, the following choices are available:
 - 1. The participant may be excluded from the study;
 - 2. The participant may be included in the study if the abnormal value(s) is not clinically significant (NCS) (the investigator must annotate the laboratory value "NCS" on the laboratory safety test source document).
 - 3. The participant may be included in the study if the abnormality is consistent with a pre-existing medical condition which is not excluded per protocol (eg, elevated eosinophil count in a participant with asthma or seasonal allergies), the medical condition should be annotated on the laboratory report.

OR

- 4. The abnormal test may be repeated (refer to items a. and b. below for continuation of algorithm for repeated values).
 - a. If the repeat test value is within the normal range, the participant may enter the study.
 - b. If the repeat test value is still abnormal, the study investigator will evaluate the potential participant with a complete history and physical examination, looking especially for diseases that could result in the abnormal laboratory value in question. If such diseases can be ruled out, and if the abnormal laboratory value is not clinically relevant, then the participant may enter the study.
- D. If there is any clinical uncertainty regarding the significance of an abnormal value, the participant will be excluded from the study.

10.9 Appendix 9: Approximate Blood/Tissue Volumes Drawn/Collected by Trial Visit and by Sample Types

| Panels A, B, C, D, E | Pre-trial | Treatment Periods | Post-trial | Total Collections | mL Per Collection | Total mL/ Test |
|---|-----------|-------------------|------------|-------------------|-------------------|----------------|
| Laboratory safety tests‡ | 1 | 3 | 1 | 5 | 13 | 65 |
| Serum β -Human Chorionic Gonadotropin (β -hCG)/FSH | 1 | 0 | 0 | 1 | 5 | 5 |
| HIV/Hepatitis Screen | 1 | 0 | 0 | 1 | 5 | 5 |
| Blood for Planned Genetic Analysis | 1 | 0 | 0 | 1 | 8.5 | 8.5 |
| Blood for PBMC | 0 | 12 | 0 | 12 | 16 | 192 |
| Blood for MK-8527 | 0 | 14 | 0 | 14 | 3 | 42 |
| Blood for HIV RNA, viral resistance § | 1 | 13 | 0 | 14 | 13 | 182% |
| Approx. Total Blood Volume Per Participant for Panels A - E† | | | | | | 499.5 mL |
| † If additional safety analysis is necessary, additional blood (up to 50 mL) may be obtained. Note: never to exceed 50 mL ‡ Blood for CD4 cell count are included in the Laboratory Safety blood draw volume. § For all panels blood for HIV-1 viral RNA and viral resistance may be collected up to the post-trial visit if participants do not start ART. % An additional 4 mLs of blood may be drawn at 168 hours post-dose if ultra-deep sequencing is needed. | | | | | | |

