| | Pre-trial | Treatment | | | | | | | | | | | | | | | | | | | | | | | | Post-study | Notes |
| Scheduled Hour, Day, Week, etc. | Screening 1 | Pre-dose | 0 | 0.25 | 0.5 | 1 | 2 | 3 | 4 | 6 | 8 | 12 | 24 | 48 | 72 | 96 | 120 | 144 | 168 | 192 | 240 | 336 | 504 | 672 ₁ | Post-study ^k | | |
| Orthostatic Vital Signs (heart rate, blood pressure) | X | X | | | | X | | | | | | | X | | | | | | X | | | | | | | X | |
| 12-lead ECG | X | X ^m | | | | X | | | | | | | X | | | | | | X | | | | | | | X | |
| Urine/Serum β-Human Chorionic Gonadotropin (β-hCG; WOCBP only) ^e | X | X ^d | | | | | | | | | | | | | | | | | | | | | | | | | |
| Serum Follicle Stimulating Hormone (FSH) - (WONCBP only) ^f | X | | | | | | | | | | | | | | | | | | | | | | | | | | |
| HIV, hepatitis B and C screen (per site SOP) | X | | | | | | | | | | | | | | | | | | | | | | | | | | |
| Urine Drug Screen (per site SOP) ^g | X | X | | | | | | | | | | | | | | | | | | | | | | | | | |
| Hematology, Urinalysis, Chemistry | X | X ^d | | | | | | | | | | | X | | | | | | X | | | | | | | X | |
| AE/SAE review | X-----X | | | | | | | | | | | | | | | | | | | | | | | | X | | |
| Pharmacokinetics | | | | | | | | | | | | | | | | | | | | | | | | | | | |
| Blood for Plasma MK-8527 Assay ^h | | X | | | X | X | X | X | X | X | X | X | X | X | X | X | X | | X | | | | | | | | |
| Blood for MK-8527 PBMC Assay ⁱ | | X | | | | | | | X | | | X | X | | X | X | X | X | X | | X | X | X | X | X | X | |
| Pharmacodynamics | | | | | | | | | | | | | | | | | | | | | | | | | | | |
| Blood for HIV RNA, viral resistance ^j | X | X | | | | | | | X | | | X | X | | X | X | X | X | X | X | X | X | X | X | X | X | |
| CD-4 cell count | X | | | | | | | | | | | | | | | | | | | | | | | | | | |
| Biomarkers | | | | | | | | | | | | | | | | | | | | | | | | | | | |
| Blood (DNA) for Genetic Analysis ^b | | X | | | | | | | | | | | | | | | | | | | | | | | | Collected from randomized participants only – See Section 8.8 and 8.9. | |

| All Panels ^a | | | | | | | | | | | | | | | | | | | | | | | | | | |
|---|-------------|-----------|---|------|-----|---|---|---|---|---|---|----|----|----|----|----|-----|-----|-----|-----|------------|-------|-----|------------------|-------------------------|--|
| | Pre-trial | Treatment | | | | | | | | | | | | | | | | | | | Post-study | Notes | | | | |

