8 STUDY ASSESSMENTS AND PROCEDURES

- Study procedures and their timing are summarized in the SoA.
- Adherence to the study design requirements, including those specified in the SoA, is essential and required for study conduct.
- The investigator is responsible for ensuring that procedures are conducted by appropriately qualified or trained staff. Delegation of study site personnel responsibilities will be documented in the Investigator Study File Binder (or equivalent).
- All screening evaluations must be completed and reviewed to confirm that potential participants meet all eligibility criteria. The investigator will maintain a screening log to record details of all participants screened and to confirm eligibility or record reasons for screening failure, as applicable.
- Procedures conducted as part of the participant's routine clinical management (eg, blood count) and obtained before signing of ICF may be utilized for screening or baseline purposes provided the procedure met the protocol-specified criteria and were performed within the time frame defined in the SoA.
- Additional evaluations/testing may be deemed necessary by the investigator and or the Sponsor for reasons related to participant safety. In some cases, such evaluation/testing may be potentially sensitive in nature (eg, HIV, Hepatitis C), and thus local regulations may require that additional informed consent be obtained from the participant. In these cases, such evaluations/testing will be performed in accordance with those regulations.

The maximum amount of blood collected from each participant over the duration of the study will not exceed approximately 499.5 mL (see Appendix 9).

Repeat or unscheduled samples may be taken for safety reasons or for technical issues with the samples.

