9.4 Analysis Endpoints

Primary Pharmacodynamic

The primary pharmacodynamic variables in this study include plasma HIV -1 RNA pre-dose and 4, 24, 96, 120, 144, 168, 240, 336, 504 and 672 hours post-dose.

Primary Safety

The primary safety endpoints in this study include all types of AEs, in addition to laboratory safety assessments, ECGs, and VS.

Secondary Endpoints

The secondary endpoints in this study include AUC_{0-168hr}, T_{max}, C_{max}, C_{168hr}, apparent terminal t_{1/2} for both MK-8527 plasma and MK-8527-TP in PBMC following single oral administration of MK-8527 on Day 1.

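### Appendix 9 counts one draw fewer than the Schedule of Activities for PBMC, plasma MK-8527 and HIV RNA, so the full schedule without ART comes to 531.5 mL against a stated maximum of about 499.5 mL

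*Combined protocol and SAP*

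**What the plan says.** Appendix 9 lists, for each sample type, the pre-trial, treatment and post-trial collections, the total number, the mL per collection and the total mL. The PBMC row is "Blood for PBMC | 0 | 12 | 0 | 12 | 16 | 192" and the plasma row is "Blood for MK-8527 | 0 | 14 | 0 | 14 | 3 | 42". The HIV RNA and resistance row has 1 pre-trial and 13 treatment collections of 13 mL, 182 mL in all. The safety-laboratory row is "Laboratory safety tests‡ | 1 | 3 | 1 | 5 | 13 | 65". The table total is 499.5 mL.

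Section 8 turns that total into a limit: "The maximum amount of blood collected from each participant over the duration of the study will not exceed approximately 499.5 mL". Section 8.12.6 allows up to 50 mL more for safety, PK or PD work, but still holds each participant to the Section 8 maximum.

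The SoA rows "Blood for Plasma MK-8527 Assay" and "Blood for HIV RNA, viral resistance", and the PBMC row between them, each carry a predose mark. Section 9.4 also names the predose value among the primary pharmacodynamic variables: plasma "HIV -1 RNA pre-dose and 4, 24, 96, 120, 144, 168, 240, 336, 504 and 672 hours post-dose".

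Three SoA footnotes bear on the late draws. Footnote i allows PBMC sampling up to the post-trial visit whether or not ART has begun. Footnote j allows viral-load sampling up to that visit only if ART has not begun. Footnote l lets the 672 h sample be taken at the post-trial visit. Section 4.1 places the last viral-load draw on the day ART starts, before its first dose.

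**The concern.** The treatment-period counts in Appendix 9 (12 PBMC, 14 plasma, 13 HIV RNA) equal the postdose marks in the SoA exactly, which leaves no room for the predose marks. The table does not exclude predose draws by convention, because its three treatment-period safety-laboratory collections are predose, 24 h and 168 h.

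What is at stake is a figure used as a cap for each participant. Section 8 states it and Section 8.12.6 depends on it. For scale, exclusion criterion 8 treats about 500 mL as one unit of blood. If the budget is short, a site that follows the whole SoA can exceed the cap with no unscheduled sampling at all. No endpoint definition or analysis method is affected.

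**Working it through.** **1. Reproduce the stated total.** Collections × mL per collection, from Appendix 9:

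- safety laboratory 5 × 13 = 65
- beta-hCG/FSH 1 × 5 = 5
- HIV/hepatitis screen 1 × 5 = 5
- genetic sample 1 × 8.5 = 8.5
- PBMC 12 × 16 = 192
- plasma MK-8527 14 × 3 = 42
- HIV RNA 14 × 13 = 182

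Sum: 65 + 5 + 5 + 8.5 + 192 + 42 + 182 = 499.5 mL. The arithmetic is right on the table's own counts.

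**2. Count the SoA marks against the header times, up to 672 h.**

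| Sample | SoA marks | SoA count | Appendix 9 count |
|---|---|---|---|
| Plasma | predose; 0.5, 1, 2, 3, 4, 6, 8, 12, 24, 48, 72, 96, 120, 168 h | 1 + 14 = 15 | 14 |
| PBMC | predose; 4, 12, 24, 72, 96, 120, 144, 168, 240, 336, 504, 672 h | 1 + 12 = 13 | 12 |
| HIV RNA | screening; predose; the PBMC postdose times plus 192 h | 1 + 1 + 13 = 15 | 1 + 13 = 14 |

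Each row is one draw short. The 672 h and post-study draws are counted once, as footnote l allows. This agrees with the zero that Appendix 9 puts in its post-trial column for PBMC and plasma, and for HIV RNA.

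**3. Recompute.** PBMC 13 × 16 = 208; plasma 15 × 3 = 45; HIV RNA 15 × 13 = 195.

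65 + 5 + 5 + 8.5 + 208 + 45 + 195 = 531.5 mL.

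Excess: 531.5 − 499.5 = 32 mL (= 16 + 3 + 13), and 32 / 499.5 = 6.4%. Without the beta-hCG/FSH sample: 531.5 − 5 = 526.5 mL.

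**4. Effect of starting ART.** Viral-load draws after the start fall away; PBMC draws may continue.

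- Start at 336 h (504 and 672 h viral load not drawn): 531.5 − 2 × 13 = 505.5 mL, which is 6 mL (1.2%) over.
- Start at 240 h (336, 504 and 672 h not drawn): 531.5 − 3 × 13 = 492.5 mL, which is 7 mL under.
- Without the beta-hCG/FSH sample these become 500.5 and 487.5 mL.

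**The case against.** The strongest reply is that 531.5 mL is not the planned path. Section 4.1 describes ART starting as planned on Day 10 to 14, and Section 6.5 says all participants will be encouraged to start it. On that path the total falls on either side of a limit that is itself worded as approximate. This stands, and it rules out saying that a typical participant exceeds the cap.

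Second, the late draws are permitted rather than compulsory: footnotes i and j say that samples may be collected. This also stands, so a reader should not infer that compulsory draws alone break the limit. But Section 4.1 makes ART optional, and a stated maximum has to cover a participant who gives every sample the SoA allows.

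Third, the cause is inferred. Appendix 9 places the genetic sample under pre-trial although the SoA marks it predose, so the single pre-trial HIV RNA collection could be the predose one, with screening left out. That is possible for the HIV RNA row. PBMC and plasma show zero pre-trial collections, and all three totals are one short on any reading.

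Fourth, the 50 mL allowance might seem to absorb the difference. Appendix 9 ties it to additional safety analysis. Section 8.12.6 widens it to PK and PD but keeps the Section 8 maximum in force. Scheduled draws are not additional blood.

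Fifth, the SoA columns after 672 h are misaligned in the available text. Treating post-study PBMC and HIV RNA as separate draws would add 16 + 13 = 29 mL and give 560.5 mL, but that figure rests on those columns and is not relied on here.

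**Conclusion.** Appendix 9 is wrong as written: three rows are each one draw short of the SoA, and the total carried into Section 8 is 32 mL (6.4%) too low for a participant who completes the schedule without ART. The missing draw is most likely predose, but the size does not depend on that.

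The 531.5 mL figure assumes every scheduled sample is taken, ART is not started, the beta-hCG/FSH sample is drawn, and the 672 h and post-study draws are one. Whether a given participant exceeds about 499.5 mL depends on whether and when ART starts, with 505.5 mL at 336 h and 492.5 mL at 240 h.

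A reader might go further and infer that sites will drop the 504 h and 672 h samples to stay within the cap. Nothing in the documents says so. The finding is an incorrect participant-level limit that should be reconciled with the schedule; it is not evidence that an endpoint is compromised.

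**What to change.** Correct Appendix 9 to PBMC 13 collections (208 mL), plasma MK-8527 15 (45 mL) and HIV RNA 15 including screening (195 mL), total 531.5 mL. Restate the Section 8 maximum to match, and note that the total is lower when ART is started. Section 8.12.6 then refers to a figure consistent with the SoA. Check that any blood volume given to participants agrees; the consent pages were not available for this review.

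Viral-load draws should not be deleted to fit 499.5 mL. Removing those at 12, 72 and 192 h, which Section 9.4 does not list, would give 531.5 − 3 × 13 = 492.5 mL. But Section 4.2 sets out to describe the kinetics of viral-load reduction, and Section 9.6 allows exploratory analyses before 168 h. The mismatch between Section 9.4 and the SoA is a separate matter to reconcile.

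The cost is three table rows, one total and one sentence, and a stated blood volume that looks slightly less favourable. Sampling and analysis do not change.

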10.10 Appendix 10: Abbreviations

| Abbreviation | Expanded Term |
|--------------|---|
| AE | Adverse experiences |
| ART | Anti-retroviral therapy |
| BSEP | Bile salt export pump |
| BMI | Body Mass Index |
| CRF | Case Report Form |
| CRU | Clinical research unit |
| DNA | Deoxyribonucleic acid |
| ECG | Electrocardiogram |
| ECI | Event of clinical interest |
| eCRF | Electronic Case Report Form |
| EDC | Electronic data collection |
| EM | Exposure multiple |
| EMA | European Medicines Agency |
| FBR | Future Biomedical Research |
| FSH | Follicle stimulating hormone |
| GCP | Good Clinical Practice |
| GM | Geometric mean |
| GMR | Geometric mean ratio |
| HED | Human equivalent dose |
| HIV-1 | Human immunodeficiency virus type-1 |
| IB | Investigator's Brochure |
| ICF | Informed Consent Form |
| ICH | International Conference on Harmonization |
| IRB | Institutional Review Board |
| NOAEL | No observed adverse effect level |
| NRTI | Nucleoside reverse transcriptase inhibitor |
| NRTTI | Nucleoside reverse transcriptase translocation inhibitor |
| OAT1 | Organic anion transporter 1 |
| OAT3 | Organic anion transporter 3 |
| OATP1B1 | Organic anion transporting polypeptide 1B1 |
| OCT2 | Organic cation transporter 2 |
| PD | pharmacodynamics |
| PK | Pharmacokinetic |
| POC | Proof-of-concept |
| QP2 | Department of quantitative pharmacology and pharmacometrics |
| RNA | Ribonucleic acid |
| SAD | Single ascending dose |
| SAE | Serious adverse event |
| SoA | Schedule of activities |
| SUSAR | Suspected unexpected serious adverse reaction |
| TP | Triphosphate |
| UDS | Urine drug screen |
| VL | Viral load |
| WOCBP | Woman/women of childbearing potential |

